14.6 Reporting and Exclusions

14.6.1 Evaluation of toxicity.

All participants will be evaluable for toxicity if they received any protocol therapy.

14.6.2 Evaluation of response.

All participants randomized on the study who have RECIST measurable disease must be assessed for response to treatment, even if there are major protocol treatment deviations, or they receive no treatment, or if they are ineligible. Participants who have no follow-up tumor evaluations, who die or receive non-protocol anticancer therapy before a response is noted, or who have unknown or not-assessable response will count as non-responders.

CONFIDENTIAL

This document is confidential. Do not disclose or use except as authorized.

14.6.3 Evaluation of progression-free survival.

All participants randomized on the study must be assessed for PFS, even if there are major protocol treatment deviations, or they receive no treatment, or if they are ineligible. However, there will be no imputation of any missing progression-free survival times.

14.6.4 Analyses of Subsets of Patients.

For all endpoints except toxicity, the primary analysis will be based on all randomized patients (and the primary analysis of toxicity will be based on all patients who receive at least one dose of one of the study agents). However, in addition to the primary analysis, analysis of subsets of patients may be done (e.g., analysis restricted to eligible patients or to patients who receive at least one cycle of therapy). However, these analyses of subsets will be considered exploratory and will not serve as the basis for drawing conclusions about treatment efficacy.

15. PUBLICATION PLAN

The data will be collected and analyzed by [name], in conjunction with a DFCI biostatistician, and key co-investigators. The results will be shared with Synta Pharmaceuticals. It is anticipated that results will be made public within 12 months of the end of data collection. Initial release may be an abstract that meets the requirements of the International Committee of Medical Journal Editors. The primary endpoint of the study will not be reported until the study is closed to accrual and the protocol-specified follow up period has elapsed. A report will also be published in a peer-reviewed journal. A full report of the outcomes will be made public no later than three years after the end of data collection.

Appendix A: Performance Status Criteria

ECOG Performance Status Scale		Karnofsky Performance Scale	
Grade	Description	Percent	Description
0	Normal activity. Fully active, able to carry on all pre-disease performance without restriction.	100	Normal, no complaints, no evidence of disease.
		90	Able to carry on normal activity; minor signs or symptoms of disease.
1	Symptoms, but ambulatory. Restricted in physically strenuous activity, but ambulatory and able to carry out work of a light or sedentary nature (e.g., light housework, office work).	80	Normal activity with effort; some signs or symptoms of disease.
		70	Cares for self, unable to carry on normal activity or to do active work.
2	In bed < 50% of the time. Ambulatory and capable of all self-care, but unable to carry out any work activities. Up and about more than 50% of waking hours.	60	Requires occasional assistance, but is able to care for most of his/her needs.
		50	Requires considerable assistance and frequent medical care.
3	In bed >50% of the time. Capable of only limited self-care, confined to bed or chair more than 50% of waking hours.	40	Disabled, requires special care and assistance.
		30	Severely disabled, hospitalization indicated. Death not imminent.
4	100% bedridden. Completely disabled. Cannot carry on any self-care. Totally confined to bed or chair.	20	Very sick, hospitalization indicated. Death not imminent.
		10	Moribund, fatal processes progressing rapidly.
5	Dead.	0	Dead.

CONFIDENTIAL

This document is confidential. Do not disclose or use except as authorized.

CONFIDENTIAL

This document is confidential. Do not disclose or use except as authorized.

DFCI personnel will be responsible for making sure that that patient has obtained a blue card (obtained via [contact], that images are available for the CSIR team to review in advance of the Percipio request, arranging for appropriate blood work to be drawn (PT/INR, PTT, CBC), and notifying patients that 1) they should be expected to arrive 1 hr in advance of the biopsy, 2) the procedure will take approximately one hour, and 3) the recovery may last 4-6 hours or longer. Also they should be notified that someone will need to be available to drive them home. Additional instructions will be provided by the CSIR nursing staff. For questions, call CSIR coordinators at [contact]. DFCI team will be present for procedure and to transport tissue, provide materials, fixatives, and requisitions. The DFCI study coordinator will receive and transport research specimens to the appropriate labs.

CONFIDENTIAL

This document is confidential. Do not disclose or use except as authorized.

Special Needs: Off Coumadin x 5 days and then recheck labs. Patients should be off ASA for at least 5 days, or heparin (e.g., fragmin, Arixtra (LMW Heparin compound)) or NSAIDs for more than 48 hours. If there are risks of stopping these medications, these should be discussed with other care providers by DFCI personnel before the referral to CSIR.

Billing: Funding is provided by a Komen grant. F # 8151631. Contact for billing: [name] or [name], Clinical Trials Business Office, Ph [contact] or [contact], DFCI BP332A.

Note: Less than the goal quantity of tissue is accepted for each type of biopsy, and will be left to the clinical judgment of the physician performing the procedure. **Procedure (if not bone):**

Set	Needle	# Sample	Preparation	Destination
1	18-20G cores*	3-6	Dry/cup	DFCI SM932 DFCI [name] for pick up/processing.

*use 18G if safe to do so. Can use 20G or obtain fewer specimens, at discretion of interventionalist for safety reasons

*if for safety reason only 22G fine needle aspiration biopsies are thought possible (whether per treating physician or interventionalist), then use the following protocol:

Set	Needle	# Sample	Preparation	Destination
1	FNAB	3*	*	DFCI SM932 DFCI [name] for pick up/processing.

*Special notes regarding sample collection/preparation:

1. One pass should be evacuated and rinsed directly into 2mL of room temperature Trizol for RNA analysis.
2. One pass should be evacuated and rinsed directly into 2mL of room temperature Trizol for DNA or RNA analysis.
3. One pass should be evacuated and rinsed directly into 10-20mL of RMPI to prepare a cell block

Procedure (bone ONLY):

Set	Needle	# Sample	Preparation	Destination
1	11-13G	1-3	Dry/cup	DFCI SM932 DFCI [name] for pick up/processing.

Procedure (Paracentesis or Thoracentesis)

Set	Needle	# Sample	Preparation	Destination
1	*	500cc	Standard collection tube/bottle	DFCI SM932 DFCI [name] for pick-up/processing

*As clinically indicated.

SGS rev 6-18-12

APPENDIX C:

Tissue and Blood Acquisition Guidelines

FOR DANA FARBER CANCER INSTITUTE AND BRIGHAM & WOMEN'S HOSPITAL LAB USE ONLY

For Biopsies of Soft Tissue, Liver, Bone, Breast, Etc.

1. After biopsy is performed, the tissue mass is placed on a sterile gauze
2. Using forceps, separate the tumor tissue
3. Place 2 pieces (cores) of tumor tissue on a pre-frozen bed of OCT in each cassette (typically end up with 3 cassettes per biopsy); the last cassette will contain many small pieces of tumor tissue
4. Fill cassettes with OCT
 - a. Completely cover tissue with additional OCT
 - b. Limit the amount of bubbles
5. Tissue must be frozen immediately by placing cassettes on dry ice in a biohazard cooler
6. Transport samples to the lab (Smith building, 9th floor, Room SM-948) and complete freezing of samples in OCT with dry ice (about 10 minutes freezing time)
7. Once samples are frozen, place in plastic bag; label bag with date, protocol number, patient number, and number of initials included
8. Store in -80C freezer

For Effusions and Ascites

Email notification should be sent to [name] at [contact] to arrange sample pick up.

Samples are to be collected in a sterile vacutainer.

The coordinator will pick up ascites/ pleural fluid from BWH Cytology for cell pellet processing in [name] lab (Smith building, 9th floor, Room SM-948)

Fluid sample should be split into three equal aliquots.

One aliquot should be spun down into a pellet and snap frozen in an ETOH/dry ice bath or in liquid N₂. This sample is stored in [name] lab and should be registered in caTissue Blood Tissue Bank.

One aliquot should be spun down into a pellet and fixed by [name] lab, and processed as a standard cell block by the Specialized Histopathology Services at BWH (Thorn building, 6th floor, Rooms 604/603B). The request for a standard cell block is submitted online through the DF/HCC Research Pathology Cores website: <http://genepath.med.harvard.edu:8080/pathcore/> and it should specify: Specialized Histopathology Services (SHL): Cell paraffin block preparation from ascites/pleural fluid. Then, the fixed sample is taken to the Specialized Histopathology Services at BWH for processing as a standard block along with a print out of request, (Note: if the sample preparation is done by a clinical cytopathology laboratory, it is important to explain that the sample is for research purposes only and that no thin prep should be performed as this uses up a significant portion of the sample.)

One aliquot should be spun down into a pellet that should be washed and re-suspended in PBS, and then transferred into Cell Save preservative tubes (7.5 mL) in the research lab. Samples should be submitted together with a Circulating Tumor Cell Core Facility request form to BWH CTC Core Facility.

Pleural fluid samples can be transported and stored at room temperature (15-30 °C) up to 72 hours before processing. Do not refrigerate or freeze the sample. Samples must be processed within 72 hours of collection, but best results are obtained if the sample is processed as soon as possible.

For Fine Needle Aspiration Samples

For patients who undergo fine needle aspiration (FNA), 3 passes should be collected:

The first pass should be evacuated and rinsed directly into 2mL of room temperature Trizol to collect the RNA; a second pass should be evacuated and rinsed directly into another 2mL of room temperature Trizol to collect the DNA; the last pass should be evacuated and rinsed directly into 10-20mL of RPMI and prepared as a cell block.

The 2 samples suspended in trizol are to be brought to [name] in [name] lab (Smith 486) for RNA & DNA analysis. The 1 aliquot in RPMI should be spun down into a cell pellet, washed and resuspended in ethanol (by [name] lab), and brought to Cytopathology:

Brigham and Women's Hospital
[name]
c/o [name]
[contact]

Appendix H should accompany the sample. Sample should be labeled with a BOT number (assigned by [name] lab; must be requested from [name]).

[name]'s team will create the block and send it to Histology to embed in paraffin. When complete (appx 24 hours), the block is ready for pickup.

Block is picked up Amory 3 Histology in BWH.

For CTC Samples

Blood samples are to be collected at the timepoints specified in the Specimen Submission Calendar (Section 9.5). Samples may be drawn Monday through Friday but not the day before a holiday (unless prior arrangements to receive the sample have been made).

1. Samples are to be collected in Cell Save preservative tubes (7.5 mL). Label tube with sample identifier / study ID number, protocol number, time point, and date of collection.
2. Draw a minimum of 5 mL of blood/tube (required in order to process the sample).
3. Gently invert each tube 4 times to ensure proper mixing of the blood with the fixative.
4. Blood samples can be shipped/transported and stored at room temperature (15-30 °C) up to 72 hours before processing. Do not refrigerate or freeze the sample. Samples must be processed within 72 hours of collection, but best results are obtained if the sample is processed as soon as possible. Samples should be submitted with a CTC request form. Do not submit clotted samples or samples containing less than 4ml of blood. Samples should be shipped by same day courier or overnight parcel directly to:

Dana-Farber Cancer Institute
Attn: [name]
[name]
[name]

Email notification should be sent to [contact] prior to shipment of sample. [name] will send a reply email to confirm receipt of the sample.

Blood for Germline DNA

One 10 mL lavender top tube will be collected at baseline and banked in order to extract germline DNA to be used as normal DNA reference for tumor tissue-based studies.

Blood for cfDNA:

One 10 mL Streck tube will be collected at the timepoints specified in Section 9.5, Specimen Submission Calendar. The tube must be filled completely and gently inverted 8-10 times immediately after collection. Blood collected in the Streck tube can be stored for 14 days between 6-37 degrees C and can be mailed at room temperature.

Blood for PBMC samples

Blood will be drawn into two PAXgene blood RNA tubes (ref #762165) from Qiagen/BD. After the blood draw, samples will sit at room temperature for two hours and then sit for 24 hours in a -20° C freezer. Following this, samples will be stored at -80° C until several samples have accumulated. Blood samples are to be collected at the timepoints specified in Section 9.5, Specimen Submission Calendar. Samples will be stored at -80° C until pick-up is coordinated with a member of [name] laboratory at Whitehead Institute for Biomedical Research in Cambridge, MA.

CIRCULATING TUMOR CELL CORE LABORATORY - REQUISITION FORM

[name]., Director

[name]

[name]

[contact] [contact] [contact]

REQUIRED CLIENT INFORMATION:

Principal Investigator _____

Additional Contact _____

Results via mail, fax, or both: _____

Address _____

Fax _____

Email _____

Telephone _____

Billing Information :

Partners Institutions:

PeopleSoft Business Unit: _____

Fund # _____

Partners Fund end Date: _____

All Others (including DFCD):

Email Invoice to: _____

Tube	Sample ID #	Protocol #	Draw Date	Draw Time	Service Requested (check one)*
1		11-477			 Enumeration  Profile Kit (select one)  cytospin - methanol fixation  cytospin - 3:1 fixation  cytospin - air dried  tube
2		11-477			 Enumeration  Profile Kit (select one)  cytospin - methanol fixation  cytospin - 3:1 fixation  cytospin - air dried  tube
3		11-477			 Enumeration  Profile Kit (select one)  cytospin - methanol fixation  cytospin - 3:1 fixation  cytospin - air dried  tube

* Enumeration uses an Epithelial Cell Kit and provides a numerical result.

* Profile Kit isolates cells for downstream analysis.

For Lab Use Only:

Date and time processed
Initials/Comments

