In the dose-escalation 9090-02 trial, blood samples were obtained on C1D1 and C1D15 to quantitate HSP70 RNA levels. Maximum induction occurred in the sample acquired 1.5 to 2 hours after the start of infusion but reached a plateau at low ganetespib levels, suggesting that this may be an overly sensitive biomarker of ganetespib activity.

Drug Interactions

Inhibition and induction potentials of STA-9090 were investigated in human liver microsomes and human hepatocytes. STA-9090 was an inhibitor of CYP2C19 and CYP3A4 (midazolam-specific) but was not an inducer of CYP or UGT isozymes.

At clinically relevant concentrations, STA-9090 inhibited UGT-mediated metabolism to some extent, but not CYP2C9 or CYP3A4-mediated metabolism of potential co-medications in human hepatocytes. STA-9090 did not significantly affect the CYP3A4-mediated metabolism of atorvastatin, dexamethasone, fentanyl, and warfarin, or CYP2C9-mediated metabolism of warfarin. Inhibition of CYP1A2, CYP2B6, CYP2D6, and CYP3A4 (testosterone-specific) were less than 50% at concentrations up to 10 μ M.

Based on the Caco-2 permeability assay, STA-9090 is a potential P-gp substrate. As per Chouinard, et.al, fulvestrant is glucuronidated by UGT1A1, 1A3, 1A4 and 1A8 and ganetespib has been shown to inhibit UGT-mediated metabolism of furosemide (UGT1As); however, laboratory work completed at Synta specifically addressing possible UGT-mediated interactions with ganetespib indicates that an alteration of fulvestrant metabolism by ganetespib is unlikely. Fulvestrant metabolism is unaffected by the presence of ganetespib at ganetespib concentrations of 1, 10, and 20 μ M in human hepatocytes *in vitro*. For reference, at 216

CONFIDENTIAL

This document is confidential. Do not disclose or use except as authorized.

mg/m² ganetespib, C_{max} is approximately 16 μM. At 150 mg/m² it is approximately 11 μM (9090-02)

Synta also addressed DDI potential from the perspective of a possible effect of fulvestrant on ganetespib *in vitro*. There was no alteration of ganetespib metabolism by fulvestrant. Concentrations of 0.3 and 3 μM fulvestrant and 1, 10, and 20 μM of ganetespib were used.

Safety

Data available as of 20 September 2013 for Synta-sponsored studies of single-agent ganetespib in patients with solid tumors and hematologic malignancies.

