9.5.2 Tissue Biopsies

Tissue specimens will be collected from tumor lesions using standard institutional procedures. See Appendix B for standard operating procedures of biopsies through the Brigham & Women's Hospital interventional radiology service. Treating investigators should use their best judgment in approaching appropriate patients for optional biopsies at the indicated time points.

Tumor tissue may be collected at the following time points on this study:

- Baseline (OPTIONAL)
- Cycle 2 Day 9 (REQUIRED for patients with biopsy-accessible disease)
- Time of cross-over (Arm A only)—(OPTIONAL)
- Off-study/time of progression (OPTIONAL)

CONFIDENTIAL

This document is confidential. Do not disclose or use except as authorized.

Tissue Biopsy Guidelines

- **The cost of the on-treatment (Cycle 2) research biopsy will be covered by the study.** For the baseline, time of cross-over, and off-study biopsies, the research biopsy will be covered by the study if it is being done for research only. However, at these time points, it is recognized that biopsies might be considered to aid in clinical management (for example, to re-assess ER, PR, and HER2 status). In the case of a clinically indicated biopsy (with an additional “research pass”), the cost of the biopsy will be charged to the patient and/or her insurance company.
- **For Arm A patients:** The Cycle 2 Day 9 biopsy may occur +/- 3 days, and on the same day as the Cycle 2 Day 9 research blood draw. If the Cycle 2 Day 9 biopsy is missed (i.e. due to scheduling problems, procedure cancellation, etc), then it should be performed instead on Cycle 2 Day 16 +/- 3 days, and the Cycle 2 research blood tests should be rescheduled to occur around the delayed biopsy (i.e. Cycle 2 Day 15 and Cycle 2 Day 16).
- **For Arm B patients:** Obtain the Cycle 2 Day 9 biopsy 18-48 hours after the Cycle 2 Day 8 dose of ganetespib. If the Cycle 2 Day 8 dose is held for any reason (e.g. for toxicity), the Cycle 2 biopsy should be performed between 18-48 hours after the Cycle 2 Day 15 dose of ganetespib.
- Patients who undergo an attempted Cycle 2 research biopsy procedure for the purpose of this protocol, and in whom inadequate tissue is obtained, are not required to undergo a repeat biopsy in order to continue on protocol.

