- A goal of 500 cc of pleural fluid will be obtained with a standard thoracentesis procedure, with or without image guidance, according to the clinical judgment of the treating physician and clinician performing the procedure. Less than the goal amount is acceptable, and should be based upon the clinical judgment of the Investigator and the clinician performing the procedure. If more than the goal amount of fluid is obtained, then the entire specimen (with the exception of what is needed for clinical purposes, if applicable) will be stored in the tissue bank.

Ascites fluid:

- A goal of 500 cc of ascites fluid will be obtained with a standard paracentesis procedure, with or without image guidance, according to the clinical judgment of the treating physician and clinician performing the procedure. Less than the goal amount is acceptable, and should be based upon the clinical judgment of the Investigator and the clinician performing the procedure. If more than the goal amount of fluid is obtained, then the entire specimen (with the exception of what is needed for clinical purposes, if applicable) will be stored in the tissue bank.

Please note that the above are guidelines for the amount of tissue to be obtained at the baseline biopsy, and are not meant to replace clinical judgment at the time the procedure is performed. Less than the goal quantity of tissue is accepted for each type of biopsy, and will be left to the clinical judgment of the physician performing the procedure. If ascites or pleural fluid is to be used as the investigational biopsy specimen, consideration should be given to confirming the malignant nature of the ascites or pleural fluid prior to study entry.

CONFIDENTIAL

This document is confidential. Do not disclose or use except as authorized.

Risks of Research Biopsies and Procedures for Minimizing Risk

Potential risks according to site are:

Breast (core biopsy/FNA):

- Likely: local discomfort and minor bleeding.
- Less likely: moderate or major bleeding, need for blood transfusion, hospitalization due to bleeding or other complications, infection, pneumothorax, damage to adjacent organs.

Skin/chest wall (punch biopsy):

- Likely: local discomfort and minor bleeding.
- Less likely: moderate or major bleeding, or infection

Lymph node or soft tissue (core needle biopsy/FNA):

- Likely: local discomfort and minor bleeding.

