Following the biopsy of a specimen, all tissue cores will be snap-frozen in OCT compound intra-operatively. This sample handling is optimal for obtaining high quality total RNA from human tumor tissue for microarray studies. After the biopsy is performed, the tissue mass is placed on a dry sterile gauze and the tumor tissue is separated using forceps. Two pieces (cores) of tumor tissue are placed on a pre-frozen bed of OCT in each cassette, typically ending up with 3 cassettes per biopsy (the last cassette will contain many small pieces of tumor tissue). Cassettes are then filled with OCT, completely covering the tissue and limiting the amount of bubbles (forceps can be used to pop any bubbles). Tissue must be frozen immediately by placing cassettes on dry ice in a biohazard cooler; freezing of samples in OCT with dry ice takes about 10 minutes freezing time. Once samples are frozen, place in plastic bag; label bag with date, protocol number, patient number, patient initials, and number of biopsy samples included. Store in -80°C freezer until the time of shipment.

CONFIDENTIAL

This document is confidential. Do not disclose or use except as authorized.

For patients who undergo fine needle aspiration (FNA) rather than core biopsy or punch biopsy 3 passes should be collected. The first pass should be evacuated and rinsed directly into 2mL of room temperature Trizol to collect the RNA; a second pass should be evacuated and rinsed directly into another 2mL of room temperature Trizol to collect the DNA; the last pass should be evacuated and rinsed directly into 10-20mL of RPMI and prepared as a cell block.

For patients who have pleural fluid or ascites collected, samples should be collected in a sterile vacutainer. The fluid sample should be split into three equal aliquots. One aliquot should be spun down into a pellet and snap frozen in an ETOH/dry ice bath or in liquid N₂. One aliquot should be fixed and processed as a standard cell block. One aliquot should be spun down and transferred into Cell Save preservative tubes (7.5 mL) in the research lab. Fluid samples can be transported and stored at room temperature up to 72 hours before processing. Do not refrigerate or freeze the sample. Samples must be processed within 72 hours of collection, but best results are obtained if the sample is processed as soon as possible.

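### The 72-hour room-temperature rule for pleural fluid and ascites conflicts with the order to snap freeze one aliquot, so fluid used as the Cycle 2 biopsy may not reflect the 18-48 hour time point.

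*Combined protocol and SAP*

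**What the plan says.** **Timing.** For Arm B, Section 9.5.2 instructs: "Obtain the Cycle 2 Day 9 biopsy 18-48 hours after the Cycle 2 Day 8 dose of ganetespib". If the Day 8 dose is held, the same interval runs from the Day 15 dose. Section 14.5.2 explains the choice of time point: fulvestrant should be at steady state, and ganetespib should have had time to destabilize HSP90 client proteins and so change transcription downstream.

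**Fluid is an accepted specimen.** Section 9.5.2 sets collection goals for pleural fluid and ascites alongside the solid sites, and gives advice that begins "If ascites or pleural fluid is to be used as the investigational biopsy specimen".

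**Handling of fluid.** Section 9.5.2 and Appendix C (For Effusions and Ascites) have it collected in a sterile vacutainer, with no additive named, and then split into three aliquots. For the first, "One aliquot should be spun down into a pellet and snap frozen in an ETOH/dry ice bath" (or in liquid nitrogen). The second becomes a cell block. The third is spun down and moved into CellSave preservative tubes in the research laboratory. The storage rule follows. Section 9.5.2 has "Fluid samples can be transported and stored at room temperature up to 72 hours before processing"; Appendix C has "Pleural fluid samples can be transported and stored at room temperature (15-30 °C) up to 72 hours before processing". Both places then prohibit refrigeration and freezing, set 72 hours from collection as the limit for processing, and urge the earliest possible processing.

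**Handling of other specimens.** For cores, Appendix C requires: "Tissue must be frozen immediately by placing cassettes on dry ice in a biohazard cooler". Section 9.5.2 describes this kind of handling as the best for RNA quality. Two of the three fine-needle passes are rinsed directly into Trizol, for RNA and DNA; the third goes into RPMI for a cell block.

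**The concern.** Read literally, the storage rule covers the whole fluid sample: it counts from collection and applies before processing. Splitting, spinning and snap freezing are the processing. A laboratory that follows the text could therefore hold the future frozen pellet at room temperature for up to three days, or could find itself told both to freeze and not to freeze the same material.

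The Cycle 2 specimen is meant to show HSF1-regulated genes, other Hsp90 targets and protein staining at a set time after ganetespib. If cells stay unstabilized well past collection, the result may partly reflect time in the tube. Fluid would then be pooled with cores frozen at once, and Section 14.5.2 has no rule that separates the two. The delay also could not be reconstructed from the shipping form. Appendix K, which covers fluid biopsy samples, asks for the date obtained but not the time, and has no field for stabilization. Appendices J and L do ask for a collection time, for CTC and PBMC tubes.

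**Working it through.** **1. The plan's own specimen count.** Section 14.5.2 assumes that 20% of patients have inaccessible disease and that 60% of biopsies are informative.
- Share with usable tissue: 0.80 × 0.60 = 0.48.
- Of the effective 60 patients: 0.48 × 60 = 28.8, which the plan gives as 28.
- Exact two-sided Fisher power at 0.05 for the four tabled differences is 82.3%, 83.3%, 84.1% and 81.3% if the 28 are split 20 + 8 (the split is not stated). This agrees with the plan's 81-84%.

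These figures are not in dispute. They show how few specimens carry the comparison.

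**2. Interval from dose to freezing for Arm B fluid.** Interval = time of collection after the dose + hold before processing.
- Shortest: 18 + 0 = 18 hours.
- Longest: 48 + 72 = 120 hours, which is 120 / 48 = 2.5 times the upper end of the window.
- Hold that takes freezing past 48 hours for fluid drawn at 18 hours: 48 − 18 = 30 hours. For fluid drawn at 48 hours, any hold does so.

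Collection stays inside 18-48 hours in every case. What is not secured is stabilization inside that window.

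**3. Specimen types side by side.**

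| Specimen | First stabilizing step | Stated limit before it |
|---|---|---|
| Core | Frozen in OCT | Immediate |
| FNA passes 1 and 2 | Trizol | Immediate |
| FNA pass 3 | Spun from RPMI, resuspended in ethanol (Appendix C) | None |
| Fluid, frozen pellet | Snap frozen | 72 hours at room temperature |
| Fluid, cell block | Fixed | 72 hours at room temperature |

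**4. Probable origin of the rule.** In Appendix C (For CTC Samples), nearly the same storage text governs blood drawn into CellSave tubes, where the preceding step is "Gently invert each tube 4 times to ensure proper mixing of the blood with the fixative". In both fluid sections the storage rule comes after the CellSave aliquot. A ban on freezing fits material in that preservative and does not fit an aliquot that must be snap frozen. The likeliest reading is that the rule was meant for the CellSave aliquot alone, but neither section says so.

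**The case against.** The strongest reply is that this is misplaced wording with little practical effect. Seventy-two hours is a ceiling, and both sections press for prompt processing. At the lead site, Appendix C arranges pick-up by email, and the interventional radiology instructions in Appendix B have the study team present to transport material. The 72-hour allowance is the same in both arms. Since 30 April 2014 only patients with measurable disease may enter, and effusions and ascites do not count as measurable, so later patients also have another lesion, though it may not be accessible to biopsy. All of this stands, and it is why the point is minor. It does not remove the conflict: no limit shorter than 72 hours is given for the frozen or cell-block aliquots.

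Several stronger readings are tempting, and the documents do not support them:
- *A fluid result is not an 18-48 hour result.* Collection is in the window, and fluid processed promptly does represent it. The result may fail to do so; it need not.
- *Drug half-life or the HSP70 response shows how fast the signal decays.* The half-lives are plasma values in patients. Section 2.1 reports of HSP70 RNA in blood that "Maximum induction occurred in the sample acquired 1.5 to 2 hours after the start of infusion", again in patients and long before 18 hours. Neither describes cells in a tube.
- *The loss of arm difference or power can be calculated.* Any such figure needs the number of fluid specimens and the degree of signal loss in each. The documents give neither.
- *Fluid alone has an open delay.* The FNA pass in RPMI has no stated limit either.
- *The fluid is certainly unpreserved.* No additive is named; that is all the text shows.

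**Conclusion.** The point holds as a minor internal conflict. The written rule lets the interval from dose to stabilization run to 120 hours for fluid used as the Arm B Cycle 2 biopsy, and it contradicts the instruction to snap freeze one aliquot. Gene-expression and immunohistochemistry results from such fluid may not reflect the intended time point. Appendix C's storage sentence names pleural fluid only; for ascites the point rests on Section 9.5.2.

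The size of the effect is unknown. It depends on how many of the roughly 28 usable specimens are fluid, how long they are actually held, and how much expression changes meanwhile; none of these is in the documents. The Cycle 2 comparisons are exploratory and hypothesis-generating under Section 1.4.2. The primary PFS analysis and the primary correlative analysis of HSF1 in archival tissue do not use these specimens and are unaffected.

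**What to change.** - In Section 9.5.2 and Appendix C, limit the 72-hour allowance and the ban on refrigeration and freezing to the aliquot in a CellSave tube.
- Require the snap-frozen and cell-block aliquots to be spun and frozen or fixed promptly on the day of collection, within a limit set by the laboratory. The documents give no basis for a particular number of hours.
- Add collection time and stabilization time to Appendix K for fluid samples.
- In Section 14.5.2, state that fluid stabilized after the limit will be flagged, and that the Cycle 2 gene-expression and immunohistochemistry comparisons will be repeated without it as a sensitivity analysis. Routine exclusion is not needed with so few specimens.

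The cost is revised wording in the two handling sections, extra fields on one form, one sentence in the analysis plan, slightly more laboratory record-keeping, and possibly a few flagged specimens.
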